2.6 Analysis of the key secondary objective

The key secondary objective was to assess the complete response rate at the end of 24 weeks of dose-titration and treatment with LCI699 in the initial single-arm, open label part of this trial.

The key secondary efficacy variable is the proportion of complete responders at Week 24. A complete responder is defined as an enrolled patient who has $mUFC \leq ULN$ at Week 24 and the dose of LCI699 during Study Period 2 (Weeks 13-24) was not increased above the level established at the end of Study Period 1 (Week 12). Dose reductions and temporary dose interruptions for safety reasons do not preclude patients from being complete responder for the key secondary endpoint. Enrolled patients who had missing mUFC assessment at Week 24 will be counted as non-responders for the key secondary endpoint.

For the key secondary objective, the statistical null hypothesis states that the complete response rate at week 24 LCI699 is $\leq 30\%$. The analysis of the key secondary objective will be based on the 2-sided 95% exact confidence interval (Clopper-Pearson method). If the lower bound of this 95% confidence interval is $\geq 30\%$, the null hypothesis will be rejected and the complete response rate will be considered at least 30% after 24 weeks of treatment with LCI699.

The above testing on the key secondary objective will only be carried out if the null hypothesis for the primary objective is rejected. This sequential procedure will ensure preservation of the overall 2-sided type 1 error at 5%.

The above analysis of the key secondary endpoint will be performed using FAS. As supportive analysis, same analysis will be performed using PPFAS.

After the interim CSR was published, additional protocol deviations were reported which affect the per-protocol population used to perform the per-protocol analyses of the key secondary

endpoint, therefore the Final CSR will report the updated result of the supportive analyses using the PPFAS.

The analyses of the key secondary endpoint using the FAS are not impacted by these additional protocol deviations, and therefore will not be reported in the Final CSR.

2.7 Analysis of secondary efficacy objectives

For the objectives identified below, the definition of Baseline/Randomization assessment and the method of computing confidence intervals are specified in Section [2.1.1.2](#) and Section [2.1.1.8](#) respectively. Last observation carried forward (LOCF) method will not be used in any of these analyses. For analysis using FAS, results will be presented by LCI699 group, Placebo group, Non-randomized patients, and All patients.

2.7.1 Compare the time-to-last control of mUFC during the randomized withdrawal period between patients randomized to continued LCI699 and placebo

The results of this objective were reported in the interim CSR, and will not be repeated for the Final CSR.

2.7.2 Assess the complete, partial, and overall response rate at Week 12, Week 24, Week 48, and during the extension period

The proportion of complete responders (enrolled patients with $mUFC \leq ULN$), partial responders (enrolled patients with $mUFC > ULN$ and at least 50% reduction from baseline), and overall responders (enrolled patients with $mUFC \leq ULN$ or have at least 50% reduction from baseline) will be summarized using point estimates for every scheduled visit in the core and extension (provided [adequate follow-up](#)) at which UFC is collected. 95% 2-sided CIs for response rates will be provided for Week 48, Week 60, Week 72 and the last available assessment of the study. The FAS will be used for the analyses.

2.7.3 Assess the change in mUFC during the core and extension period of study

For the actual value and change in mUFC from baseline during the overall study period, descriptive summaries will be provided for every scheduled visit in the core and extension (provided [adequate follow-up](#)) at which UFC is collected. The FAS will be used for the analysis.

Patients randomized to placebo during the RW period, will not have their mUFC values included in the analysis for visits at which they received placebo.

2.7.4 Assess the change in cardiovascular-related metabolic parameters associated with Cushing's disease during the core and extension period of the study

The following parameters will be analyzed: glucose, HbA1c, fasting lipid profile, SBP, DBP, weight, waist circumference and BMI).

For the actual value and change from baseline during the overall study period, descriptive summaries will be provided for every scheduled visit in the core and extension (provided [adequate follow-up](#)). The FAS will be used for the analysis.

Patients randomized to placebo during the RW period, will not have their values included in the analysis for visits at which they received placebo.

2.7.5 Assess the change from baseline in physical features of Cushing's disease by photography

For physical features of Cushing's disease, such as facial rubor, hirsutism, striae, supraclavicular fat pad, dorsal fat pad, proximal muscle wasting (atrophy), central (abdominal) obesity, and ecchymoses (bruises), the change from baseline (captured by a semi-quantitative Likert scale) at visits where photography is scheduled (Week 12, 24, 34 and 48 as well as Week 72 and EOT extension) will be assessed by shift tables. In addition, the proportion of patients having a favorable shift from baseline at post-baseline time points will also be tabulated. The FAS will be used for the analyses.

2.7.6 Assess the change from baseline in bone mineral density by DXA scan at Week 48 and the last available assessment

For bone mineral density measured by DXA scan at the lumbar spine and total hip, descriptive summaries of actual and percentage change from baseline at Week 48 and the last available assessment will be provided. The FAS will be used for the analysis.

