7.2.6 Patient reported outcomes

Three patient reported outcome instruments will be used to assess the impact of treatment on patient quality of life and symptom burden (see [Appendix 4](#)). Patients must be asked to complete each questionnaire prior to clinical assessments being undertaken, and these must be completed in accordance with the schedules listed in [Table 7-1](#) to [Table 7-3](#) and [Table 7-16](#). Patient's refusal to complete all or any part of a questionnaire should be documented in the study data capture system and should not be captured as a protocol deviation. Patient questionnaires should be completed in the language most familiar to the patient. The patient should be given sufficient space and time to complete the questionnaire. The site personnel should check the questionnaire for completeness and ask the patient to complete any missing responses. The original questionnaire will be kept with the patient's file as the source document.

Completed questionnaire(s) and any unsolicited comments written by the patient should be reviewed and assessed by the investigator for responses which may indicate potential AEs or SAEs before any clinical study examinations. This assessment should be documented in study source records. If AEs or SAEs are confirmed, study investigators should not encourage the patient to change responses reported in the completed questionnaires. Study investigators must follow reporting instructions outlined in [Section 8](#) (e.g. reference "Adverse Events" section) of the study protocol.

Table 7-16 Patient reported outcomes (PROs) collection plan

Patient Questionnaires ¹	Week	Day	Time
CushingQoL Beck Depression Inventory-II EQ-5D-5L	Mandated, week -1	Day -7 to -1	Prior to any clinical assessments or diagnostic testing.
CushingQoL Beck Depression Inventory-II EQ-5D-5L	Mandated, Week 4, 8, 12, 24, 26,28, 30,32 34, 48 (see Section 7.1)	Day 29, 57, 85, 169, 183, 197, 211, 225, 239, 337	Prior to any clinical assessments, drug dosing or diagnostic testing.
CushingQoL Beck Depression Inventory-II EQ-5D-5L	Optional Extension: Mandated, Week 72, 96, EOT extension	Day 505, 673, EOT extension	Prior to any clinical assessments, drug dosing or diagnostic testing.
¹ Patient Questionnaires should be completed in the sequence from most specific to most general: Cushing QoL → Beck Depression Inventory-II → EQ-FD-5L			

CushingQoL

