Slope (group 1)	0.427	0.031	
Slope (group 2)	0.939	0.067	
Slope (group 3)	1.635	0.017	
The value for health state 23245			1-0.9675x(0.051+0.076+0.051+0.276+0.301) =0.270

2.11.4 Secondary objective - Assess the change in Patient-Reported Outcomes (Health-Related Quality of Life) during the core and extension period of the study

Changes in PRO that are either statistically significant (based on two-sided 95% confidence interval with no adjustment for multiplicity) or exceeding the MID will be flagged.

For each of four PRO variables (CushingQoL score (2 subscale and total score), BDI total score, EQ-5D-5L utility index, and EQ-5D-5L VAS score), descriptive summaries of the actual value and change from baseline during the overall study period will be provided. The FAS will be used for this analysis.

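### The SAP drops on-placebo visits from most Final CSR summaries but not from Week 34 photography, so its All patients column mixes placebo with LCI699; the PRO section has the same gap

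*SAP*

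**What the plan says.** **Where on-placebo visits are removed.** For mUFC (SAP 2.7.3), patients randomized to placebo "will not have their mUFC values included in the analysis for visits at which they received placebo". For metabolic parameters, SAP 2.7.4 says: "Patients randomized to placebo during the RW period, will not have their values included in the analysis for visits at which they received placebo". Comparable rules cover responder denominators (2.1.1.7), average LCI699 dose (2.4.1) and scheduled safety assessments (2.8). Time-to-escape (2.7.7) leaves out the whole placebo arm.

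**Photography.** SAP 2.7.5 assesses change from baseline by shift table in the FAS, "at visits where photography is scheduled (Week 12, 24, 34 and 48 as well as Week 72 and EOT extension". It adds that "the proportion of patients having a favorable shift from baseline at post-baseline time points will also be tabulated". No exclusion follows. The opening of 2.7 states that for FAS analyses "results will be presented by LCI699 group, Placebo group, Non-randomized patients, and All patients".

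**PROs.** SAP 2.11.4 says that for each PRO variable "descriptive summaries of the actual value and change from baseline during the overall study period will be provided", using the FAS. It contains no exclusion and does not say which groups will be shown. The PRO collection plan in Protocol 7.2.6 (Table 7-16) reads "Mandated, Week 4, 8, 12, 24, 26,28, 30,32 34, 48". Weeks 28, 30, 32 and 34 therefore fall after randomization.

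**The concern.** The SAP treats a visit on placebo as uninformative about LCI699 and filters it out almost everywhere, but the filter is missing from two sections whose schedules include such visits. Followed as written, the pooled photography column at Week 34 describes neither LCI699 nor placebo. If signs return after withdrawal, that column would show a dip that a reader could take for waning effect on continued treatment.

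The sponsor expects movement of this kind in PROs. Protocol 7.2.6 and SAP 2.11.1 explain that the CushingQoL recall period was shortened to one week because symptoms are believed to change quickly once treatment stops. SAP 2.11.4 also flags PRO changes that reach significance or exceed the MID, so pooling could alter which results are flagged.

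The Placebo column has a related problem. Under Protocol 4.1.3.6, patients who leave randomized withdrawal for uncontrolled UFC resume open-label LCI699. By Week 34 that column can hold both patients on placebo and patients already re-treated.

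**Working it through.** **1. Is there a general rule that fills the gap?** No.

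| SAP section | Content | On-placebo visits |
|---|---|---|
| 2.1.1.7 | Responder proportions | Out of the denominator |
| 2.4.1 | Average LCI699 dose | Excluded |
| 2.7.3 | mUFC | Excluded |
| 2.7.4 | Metabolic parameters | Excluded |
| 2.7.5 | Photography, includes Week 34 | No rule |
| 2.7.7 | Time-to-escape | Whole placebo arm left out |
| 2.8 | Safety | Excluded |
| 2.11.4 | PROs, overall study period | No rule |

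The rule in 2.1.1.7 is confined to responders and the one in 2.8 to safety.

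**2. Planned numbers.** The documents give no figure on this point, so the planned sample size is used (Protocol 10.8, SAP 3.1): 33 per arm, 70% versus 30% response, two-sided 0.05, 87% power, 50% of enrolled patients randomized, 132 enrolled.

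Check with a continuity-corrected two-proportion calculation:
- null SE = √(2 × 0.25/33) = 0.1231; alternative SE = √(0.42/33) = 0.1128
- z = (0.40 − 1/33 − 1.96 × 0.1231)/0.1128 = 1.14, so power = 87.3%
- 66/0.50 = 132

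The stated figures reproduce.

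**3. On-placebo share of a pooled column, no dropout.**
- Week 34 photography, and PROs at Weeks 30 and 34, if the whole arm is still on placebo: 33/132 = 25%.
- Week 34, if only the 30% of placebo patients assumed to respond are still on placebo (0.30 × 33 ≈ 10) and the other 23 are back on LCI699: 10/132 = 7.6%.
- PROs at Weeks 28 and 32: Protocol Table 7-3 schedules no PRO for non-randomized patients, so a pooled column would hold randomized patients only. The share is at most 33/66 = 50%.
- Week 26 PROs are unaffected, because Table 7-16 places them before dosing.

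**4. Effect on the pooled favourable-shift proportion.** The documents give no favourable-shift rates. Assume 50% on LCI699 and 30% on placebo, with re-treated patients behaving like those on LCI699:
- 33 on placebo: (99 × 50% + 33 × 30%)/132 = 45.0%
- 10 on placebo: (122 × 50% + 10 × 30%)/132 = 48.5%

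The distortion equals the on-placebo share times the difference in rates. Other assumed rates give this range:

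| On LCI699 | On placebo | Pooled, 33 on placebo | Pooled, 10 on placebo |
|---|---|---|---|
| 50% | 30% | 45.0% | 48.5% |
| 60% | 30% | 52.5% | 57.7% |
| 60% | 50% | 57.5% | 59.2% |

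**5. After the fix.** The on-placebo share of any pooled column is 0%. Sample size, power and alpha do not change.

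**The case against.** **The by-arm columns are shown beside the pooled one.** A Week 34 dip driven by withdrawal would be visible in the Placebo photography column. This stands and limits the harm, but it does not make the pooled column interpretable.

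**The protocol has no exclusion either.** Protocol Table 3-1 names Week 34 as a photography time point, 10.5.2.5 calls for a shift table, and 10.5.7 summarizes PROs at each scheduled assessment. This is true. However, the protocol's mUFC and metabolic sections (10.5.2.3 and 10.5.2.4) carry no such exclusion for change from baseline, and the SAP added one. The inconsistency is within the SAP.

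**A reader might infer that the PRO tables will certainly have a mixed All patients column.** The documents do not say so. The sentence creating that column is in 2.7, while PROs are in 2.11. SAP 2.11.4 names no groups, and the FAS groups in 2.2 are three mutually exclusive ones without a total. The CushingQoL MID proportion is to be given by group for period 3. What is certain for PROs is the missing rule and the unnamed groups.

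**A reader might take 25% and 45% as the expected size.** They are the extreme case. Patients with mUFC above 1.5 × ULN, and at least two samples above it, must leave randomized withdrawal, so the whole arm is unlikely to be on placebo at Week 34. Patients between ULN and 1.5 × ULN do stay on placebo, so the share can also exceed 7.6%.

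**A reader might infer that the SAP declares these tables to be about LCI699 alone.** That sole focus is stated only for safety, in 2.8.

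**Conclusion.** The gap is real and narrow. For photography it follows directly from the text: Week 34 is tabulated in the FAS with an All patients column and no on-placebo exclusion. For PROs it is conditional: any pooled column at Weeks 28 to 34 would be mixed, and the SAP does not say whether there will be one.

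On planned numbers without dropout, the on-placebo share at Week 34 runs from about 7.6% to at most 25%; a pooled PRO column at Weeks 28 and 32 could reach 50%. Under assumed rates of 50% and 30%, the pooled favourable-shift proportion would be 1.5 to 5 percentage points below the rate on LCI699. The sizes depend on assumed rates and on how many placebo patients have resumed LCI699; the inconsistency does not.

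It would be wrong to read this as a threat to the trial's main conclusions. SAP 2.1 calls all Final CSR efficacy analyses supportive, without formal testing, and the primary and key secondary results do not use these summaries. This is a worthwhile clarification, not a serious defect.

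**What to change.** In SAP 2.7.5 and 2.11.4, state that values from patients randomized to placebo, at visits when they were receiving placebo, are excluded from any All patients or other pooled summary. In addition:
- keep the randomized-arm columns as defined in 2.2, with on-placebo values shown only in the Placebo column;
- flag in that column the patients who had already resumed open-label LCI699 by the visit;
- name the presentation groups for 2.11.4.

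The sentence in 2.7.4 should not be copied unchanged. It removes on-placebo values from the analysis altogether, so the Week 34 Placebo column would be left mainly with patients already withdrawn from placebo and re-treated, a selected subset. Nor should placebo-arm patients be moved into the LCI699 column when they return to drug, because 2.2 defines that group by randomization.

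The cost is a few lines of text in two sections. The filter for on-placebo visits is already needed for 2.7.3 and 2.7.4, and no new data are required.

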2.7.7 Assess the time-to-escape under treatment of LCI699

Escape is defined as the first loss of control of UFC that meets all of the following criteria:

- prior normalization of UFC has occurred ($mUFC \leq ULN$)
- both the $mUFC$ and at least 2 individual values contributing to that $mUFC$ have to be $>1.5 \times ULN$
- the loss of control of UFC is not related to a dose interruption or dose reduction due to safety reasons
- happens beyond 12-week dose titration period (Study Period 1).

Time-to-escape is defined as the time (in days) between the first UFC assessment with $mUFC \leq ULN$ and either the UFC assessment of escape (event) or last UFC assessment before permanent discontinuation of LCI699 treatment (censored), whichever occurs earlier.

For patients who attained normalization of UFC ($mUFC \leq ULN$), time-to-escape will be analyzed using K-M plot. The quartiles of time to escape and corresponding two-sided 95% confidence interval will be calculated using Kaplan-Meier methodology. In addition, time-to-escape will be summarized using descriptive statistics for patients who escape. FAS will be used for the analysis.

Patients randomized to placebo are not included in this analysis.

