Stage related to study timeline	A major subdivision of the study timeline; begins and ends with major study milestones such as enrollment, randomization, completion of treatment, etc.
Stop study participation	Point/time at which the patient came in for a final evaluation visit or when study treatment was discontinued whichever is later
Study treatment	Includes any drug or combination of drugs in any study arm administered to the patient (subject) as part of the required study procedures, including placebo and active drug run-ins. In specific examples, it is important to judge investigational treatment component relationship relative to a study treatment combination; study treatment in this case refers to the investigational and non-investigational treatments in combination.
Study treatment discontinuation	Point/time when patient permanently stops taking study treatment for any reason.
Treatment group	A treatment group defines the dose and regimen or the combination, and may consist of 1 or more cohorts.
Variable	Identifier used in the data analysis; derived directly or indirectly from data collected using specified assessments at specified time points.

Withdrawal of Consent	Withdrawal of consent from the study occurs only when a patient does not want to participate in the study any longer, and does not allow any further collection of personal data.
-----------------------	---

Amendment 5 (29-Jun-2018)

Amendment rationale

As of 25 June 2018, 91 patients are ongoing on the study. The study enrollment was completed on 22-Mar-2017.

The main purpose of this amendment is to increase the maximum duration of the optional extension period by one additional year in order to provide continued access to the study drug for those patients benefitting from the treatment until a separate long-term follow-up study is available at participating sites.

Changes to the protocol

Changes to specific sections of the protocol are shown in the track changes version of the protocol using strike through red font for deletions and red underlined for insertions.

- Glossary of terms, Section 7.1.6: the definition of the Personal Data and Withdrawal of Consent has been updated in line with the latest Novartis protocol template updated following the release of the General Data Protection Requirements (GDPR) in the European Economic Area (EEA).

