- List of abbreviations, Section 4.1.3.1, Section 6.5.2 and Section 6.5.3: Drug Supply Management replaced with Global Clinical Supply as per name change at Novartis.
- Protocol Summary, Section 6.1, Section 6.6.1, Table 6-3 and Table 6-4: clarified as 20 mg tablets supplied depending on availability.
- Section 4.1.5, Section 6.1.5: revised to extend the duration of the optional extension period and study and to include the transition timeframe to the long-term safety follow-up study or local alternative treatment option.
- Section 4.3: revised to extend the duration of the optional extension period and study.
- Section 6.5.3: corrected that the bioanalyst and the bioanalytical study monitor will also be unblinded in line with Novartis standards.
- Section 7.1.1 and Table 7-1: reference added to the Inclusion/Exclusion criteria for the eligibility assessment at screening.
- Section 7.2.1.3: revised as there was an incorrect reference to the BMI matching for the BMD T-score.
- Section 7.2.2.5, Section 10.5.3: added the central Pituitary MRI/CT assessment for tumor re-occurrence and tumor invasiveness.
- Section 7.2.3.2: corrected as placebo samples will be analyzed for this trial.
- Section 10: clarified that in this section SAS stands for Statistical Analysis System.

IRBs/IECs

A copy of this amended protocol will be sent to the Institutional Review Board (IRBs)/Independent Ethics Committee (IECs) and Health Authorities.

The changes described in this amended protocol require IRB/IEC approval prior to implementation.

The changes herein affect the Informed Consent. Sites are required to update and submit for approval a revised Informed Consent that takes into account the changes described in this protocol amendment.

Amendment 4 (06-Jul-2017)

Amendment rationale

As of 22 March 2017, 137 patients have been enrolled (treated). The study enrollment has been completed.

The main purpose of this amendment is to further increase the duration of the optional extension period in order to collect additional long-term safety and efficacy data as well as to provide continued access to the study drug for those patients benefitting from the treatment until a separate long-term safety follow-up study is set up at participating sites. Based on this extension, the end of study definition has been updated. In addition, the long-term safety follow-up study modalities have been detailed.

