In Part II, 17 out of 19 patients completed the 22 weeks treatment period and 15 of 19 (79%) had normal mUFC levels at week 22. During treatment with LCI699, the mean mUFC levels decreased quickly and stabilized to a normal level (11 to 138 nmol/24h) at Week 4 (Figure 1-5). After Week 4, normal mean mUFC levels were observed through the study up to Week 22. All patients attained UFC normalization at least once during the study, and no patient “escaped” UFC control.

Figure 1-5 Mean (+/-SE) mUFC (nmol/24h) over time by cohort

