WHO	World Health Organization

1 Introduction

The SAP document describes the planned statistical analyses for the Final CSR of study LCI699C2301 in the treatment of Cushing's disease. It incorporates analysis of the long-term safety and efficacy of the study, including data collected during both the core phase (up to Week 48) and the optional extension period. The optional extension period will end 16 months after all patients have completed Week 72 or discontinued early (prior to Week 72).

The analysis will be performed after all patients have completed the extension period or discontinued earlier.

The analysis of the core phase, including the results of the primary and key secondary outcomes was detailed in the CSR written following the DBL which occurred once all patients had completed the core phase or discontinued earlier. These details of these analyses can be found in the corresponding SAP, with cover date 06-Jul-2018.

After the interim CSR was published, additional protocol deviations were reported which affect the per-protocol populations used to perform the per-protocol analyses of the primary and key-secondary endpoints, therefore the Final CSR will report the updated results of these per-protocol analyses.

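### The escapers-only summary in SAP 2.7.7 reflects length of follow-up more than risk of escape; fixed-time Kaplan-Meier escape-free percentages would serve better at no real cost

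*SAP*

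**What the plan says.** SAP 2.7.7 defines escape as the first loss of control after normalization and after the 12-week titration period, with mUFC and at least two contributing samples above 1.5 x ULN, and not explained by a safety-related dose reduction or interruption. Time runs from first normalization to escape, or to the "last UFC assessment before permanent discontinuation of LCI699 treatment (censored), whichever occurs earlier". The population is FAS patients who normalized, and "Patients randomized to placebo are not included in this analysis".

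Three outputs are planned: a Kaplan-Meier plot; quartiles ("The quartiles of time to escape and corresponding two-sided 95% confidence interval will be calculated using Kaplan-Meier methodology"); and then "In addition, time-to-escape will be summarized using descriptive statistics for patients who escape". No escape-free percentages at fixed times are planned. There is no rule for a quartile that is not reached, and no caveat on the third output. Protocol 10.5.2.7 asks only for the Kaplan-Meier plot.

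Neither document assumes an escape rate. The nearest evidence is the 22-week part of the earlier study (Protocol 1.2.1.2.2), with 19 patients, "and no patient “escaped” UFC control". SAP 2.1 treats all efficacy analyses in the Final CSR as supportive and untested.

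**The concern.** A mean or median time among patients who escaped is bounded by how long patients were watched. It carries little information on how many escape, yet a reader may take it as a measure of durability.

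The extension has been lengthened several times by amendment, so the figure would grow between data cuts with no change in risk. SAP 2.7 also presents FAS results by group, so the continued-LCI699 and non-randomized groups could be set side by side on a statistic that cannot rank them.

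The censoring-aware numbers planned alongside it are quartiles. Even the first exists only if the Kaplan-Meier escape estimate reaches 25%. Protocol 2.2 gives long-term control without further dose escalation for escape as one of the design's aims, so a readable number for that risk is worth having.

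**Working it through.** SAP 2.7.7 states no figure to reproduce. Two questions were checked.

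**1. How the escapers-only mean behaves.** Assume a constant hazard h and complete follow-up T, so S(T) = exp(-hT). The mean time among those who escape by T is 1/h - T·S(T)/(1 - S(T)), and the true first quartile is ln(4/3)/h. Set h = -ln(1 - p)/96, where p is the proportion escaping by 96 weeks.

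For p = 10%: h = 0.10536/96 = 0.0010975 per week, so 1/h = 911.2.
- T = 96: 911.2 - 96 × 0.9/0.1 = 911.2 - 864 = 47.2 weeks.
- T = 144: S = 0.9^1.5 = 0.8538, giving 911.2 - 144 × 0.8538/0.1462 = about 70.1 weeks.

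| Escape by 96 weeks | Escapers-only mean, T = 96 | Same hazard, T = 144 | True first quartile |
|---|---|---|---|
| 10% | 47.2 wk | 70.1 wk | 262 wk |
| 20% | 46.2 wk | 68.0 wk | 124 wk |
| 40% | 43.9 wk | 62.9 wk | 54 wk |

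A fourfold risk moves the mean by 47.2 - 43.9 = 3.3 weeks. Following patients for half as long again moves it by about 23 weeks in the 10% row.

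**2. Whether the quartiles are likely to be reached.** Inputs from the documents:
- 137 patients treated (Amendment 4 rationale); about 33 planned for placebo, leaving 104 before removing those who never normalized. N = 100 was used, with N = 70 as a check.
- "As of 25 June 2018, 91 patients are ongoing on the study. The study enrollment was completed on 22-Mar-2017" (Amendment 5 rationale).
- End of extension 16 months after the last Week 72 (SAP Section 1). SAP 1.2.5 still says 4 months, so both were run.

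Assumptions: entry uniform from November 2014 to 22 March 2017; about 0.15 years to first normalization; constant escape hazard; exponential drop-out. Mean time from entry to 25 June 2018 is then 2.45 years, so the drop-out hazard is ln(137/91)/2.45 = about 0.167 per year.

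Simulated chance that each Kaplan-Meier quartile is reached, 16-month cut-off, N = 100:

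| Annual escape risk | Q1 | Median | Q3 |
|---|---|---|---|
| 2% | 2% | 0.4% | 0.1% |
| 5% | 29% | 1.5% | 0.3% |
| 8% | 82% | 6% | 0.7% |
| 10% | 96% | 14% | 0.9% |
| 20% | 100% | 96% | 16% |

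With N = 70 the pattern is the same (Q1 reached 30% of the time at 5% per year, 93% at 10%).

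At 5% per year the escapers-only median is 10.8 months at the end of core, 14.2 at Week 72 plus 4 months and 18.2 at Week 72 plus 16 months. The true median is 162 months throughout.

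**Evidence on rarity.** With 0 of 19, the one-sided 95% upper limit is 1 - 0.05^(1/19) = 14.6%, and the two-sided limit is 1 - 0.025^(1/19) = 17.6%, over 22 weeks only. This neither establishes nor excludes a low rate.

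**The case against.** The main analysis already handles censoring. The challenged sentence is an addition, openly restricted to patients who escape, and not offered as an estimate of risk. That is correct and is the main reason severity is low.

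A reader might infer that, if escape is rare, the escapers-only figure would be the only number reported. The documents do not support this. The curve is planned, and a usual descriptive summary includes the number of escapers. The planned confidence interval can have a lower limit even where the first quartile itself is not reached. Under the assumptions above and a log-log interval (the SAP names no transformation), 10% escape by Week 96 gives a first quartile in about 39% of simulated trials and a lower limit for it in about 94%. The lower limit is available in about 70% at 4% per year and 47% at 3%.

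A reader might also infer that no quartile will be estimable. That rests on rarity, which the documents do not establish, and overlooks early enrollees followed well beyond Week 96.

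It can also be said that SAP 2.7.2 and 2.7.3 cover durability through visit-wise response rates and mUFC. They do in part. But Protocol 4.1.4 allows dose increases after Week 34, so a patient who escaped and was re-controlled counts as a complete responder at later visits. Those rates are not a substitute for the risk of escape.

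Finally, fixed-time percentages can be read off the planned curve. That is true for point estimates, but not reliably for confidence limits.

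**Conclusion.** The point holds as a low-severity, free improvement. Under a constant hazard the escapers-only summary is nearly insensitive to risk (about 3 weeks' difference across a fourfold range) and lengthens with follow-up (about 47 to 70 weeks between 96 and 144 weeks at the same hazard). This does not depend on escape being rare.

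Whether the quartiles help does depend on the rate. At about 5% per year or less the first quartile is usually not reached and the median almost never is. From about 8% per year the first quartile usually is reached and the median usually is not; the median becomes likely at about 15% per year or more. These figures rest on the assumed constant hazard, entry pattern and drop-out, and on the 16-month end of extension.

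No test or trial conclusion is affected. It would be wrong to read the point as saying that the plan ignores censoring or leaves the objective without a valid analysis.

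**What to change.** In SAP 2.7.7:
- Add Kaplan-Meier escape-free percentages with 95% confidence intervals and numbers at risk at fixed times after first normalization, for example 24, 48, 72 and 96 weeks, plus the number of escapes.
- Keep the quartiles and their intervals where estimable, and state that an unreached quartile is reported as not estimable.
- Replace the escapers-only descriptive statistics with a listing of individual escape times, or keep them labelled as conditional on escape and on length of follow-up.

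The 4-month and 16-month ends of the extension (SAP 1.2.5 and SAP Section 1) should be reconciled, because they imply different follow-up and so a different escapers-only figure.

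The cost is SAP wording and one table. The estimates come from the same Kaplan-Meier fit, no new data are needed, and nothing that Protocol 10.5.2.7 requires is lost.
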